1.2.2 Dose Rationale

Ciprofloxacin

The recommended dose of ciprofloxacin for the treatment of uncomplicated UTI is 250 mg twice daily by mouth for 3 days, per the Ciprofloxacin USPI and Ciprofloxacin SmPC.

2 STUDY OBJECTIVES

2.1 Objectives

The primary objective of this study is to evaluate the clinical and microbiologic response of patients with a uUTI treated with ciprofloxacin.

The secondary objective of this study is to evaluate the validity of specific tests found on the urine dipstick as a screening tool to identify symptomatic patients with a positive urine culture, defined as growth of $\geq 10^5$ CFU/mL of a uropathogen at baseline.

3 STUDY DESIGN

This prospective, Phase 4, open label, multi-center study documents the clinical and microbiologic response of adult women patients with uUTI treated empirically with ciprofloxacin. Since UTIs in males are classified as complicated, males will not be included in this study. Approximately 250 adult women with uUTI will receive oral ciprofloxacin 250 mg twice daily for 3 days.

The primary outcome measure for efficacy evaluation will be the overall response on Day 12 (+/- 1 day). For the primary efficacy evaluation, these percentages will be based on a microbiologic-modified intent to treat population (m-MITT). The m-MITT population will be comprised of all patients who received at least one dose of ciprofloxacin and had $\geq 10^5$ CFU/mL of a baseline pathogen isolated from a urine culture specimen taken at baseline, prior to initiation of ciprofloxacin therapy.

See Appendix 1, Schedule of Activities Table.

3.1 Investigational Study Medications

Patients who present with uUTI symptoms, have a urine dipstick analysis positive for both leukocyte esterase AND nitrite who meet all of the inclusion and none of the exclusion criteria, and who agree to participate in the study, will be treated for their uUTI with ciprofloxacin.

The ciprofloxacin, or a pharmacy prescription for ciprofloxacin, will be provided to the patient by the enrolling study site. Patients will be asked to take one 250 mg tablet or capsule twice daily (day 1 to 3 + 1 day) for 3 days. In the event a patient's first dose is taken in the PM on Day 1, the patient will be expected to take an AM dose on Day 4 to complete the 6 doses of ciprofloxacin, and the EOT visit will occur on day 4 instead of day 3.

3.2 Adjunctive Systemic Antibiotics

None allowed

3.3 Additional, Non-Study Therapy Antibiotics

Concurrent use of non-study antibacterial drug therapy is permitted only if the therapy would not have a potential effect on outcome evaluations in patients with uUTI.

4 STUDY POPULATION SELECTION

Female patients who present with uUTI and who have a urine dipstick positive for both leukocyte esterase AND nitrite, and who meet all of the inclusion and none of the exclusion criteria will be eligible for participation in this study.

This study can fulfill its objectives only if appropriate patients are enrolled. The following eligibility criteria are designed to select patients for whom protocol treatment is considered appropriate. All relevant medical and non-medical conditions should be taken into consideration when deciding whether a particular patient is suitable for enrollment under this protocol.

4.1 Inclusion Criteria

- 1. Female patients ≥18 years of age with more than 24 hours of urinary symptoms attributable to a UTI
- 2. Two of the following signs and symptoms of uUTI: urinary frequency, urinary urgency, pain or burning on micturition, suprapubic pain, gross hematuria
- 3. A mid-stream urine specimen collected for the purpose of diagnosing a UTI with:
 - a. a dipstick analysis positive for nitrite AND
 - b. a dipstick analysis positive for leukocyte esterase
- 4. Has given written informed consent to participate in the study prior to Screening/Baseline (D1).

Clinical Trial Protocol: IT-004-401

4.2 Exclusion Criteria

- 1. Presence of signs and symptoms suggestive of acute pyelonephritis: fever (temperature > 38°Celsius), chills, costovertebral angle tenderness, flank pain, nausea and/or vomiting
- 2. Receipt of prior effective antibacterial drug therapy for uUTI for the presenting illness unless the recovered pathogen demonstrates resistance to initial antibiotic and clinical symptoms persist
- 3. Concurrent use of non-study antibacterial drug therapy that would have a potential effect on outcome evaluations in patients with uUTI
- 4. Patients with ileal loops or urinary stoma
- 5. Patients with an indwelling urinary catheter in the previous 30 days
- 6. Patients with paraplegia
- 7. Patients who are likely to receive ongoing antibacterial drug prophylaxis after treatment of uUTI (e.g., patients with vesico-ureteral reflux)
- 8. Any history of trauma to the pelvis or urinary tract
- 9. Patient's urine culture results, if available at study entry, identify more than 2 microorganisms regardless of colony count or patient has a potential fungal pathogen
- 10. Patient's urine culture results, if available at study entry, identifies the causative uropathogen for the presenting illness to be resistant to ciprofloxacin
- 11. Patient has severe chronic kidney disease, or is receiving hemodialysis or peritoneal dialysis or had a renal transplant
- 12. Patient is known to have severe neutropenia

Clinical Trial Protocol: IT-004-401

- 13. Patient is known to be pregnant
- 14. Patients with uncontrolled diabetes mellitus
- 15. Patients with a known history of myasthenia gravis
- 16. Patients who require concomitant administration of tizanidine
- 17. Patients with a history of allergy to quinolones
- 18. Patient is considered unlikely to survive the study period or has a rapidly progressive or terminal illness including septic shock which is associated with a high risk of mortality

4.3 Enrollment Criteria

Patients will be enrolled into the study to receive ciprofloxacin provided they have satisfied all patient selection criteria.

4.4 Women of Child-Bearing Potential

If the patient is a woman of childbearing potential, she and any male partner are required to simultaneously use 2 effective contraceptive methods, from the following list of 5:

- 1. A barrier (condoms, diaphragm or cervical cap) with spermicide;
- 2. A second, different barrier method (condoms, diaphragm or cervical cap);
- 3. Oral or similar contraceptive, which includes, but is not limited to: injectable, implanted, or patch hormone therapy, and intrauterine device (IUD) at least 7 days prior to baseline;
- 4. Documented surgical sterilization at least 4 weeks prior to baseline;
- 5. Partner vasectomy at least 6 months prior to baseline.

Clinical Trial Protocol: IT-004-401

She and any male partner must agree to continue all of these contraceptive methods until the TOC Visit. Within these limits, the specific forms of contraception employed are left to the discretion of the patient, and/or the principal investigator, and/or the patient's physician.

Women of childbearing potential include those that meet one of the following criteria:

- Females who are <45 years of age and have not had a documented hysterectomy, tubal ligation and/or bilateral oophorectomy
- Females who are >45 years of age and have not been amenorrheic for at least 1 year

5 STUDY TREATMENTS

5.1 Allocation to Treatment

This is a non-randomized, open label, multi-center study of oral ciprofloxacin in the treatment of uUTI. Approximately 250 female patients with uUTI will be administered oral ciprofloxacin twice daily for 3 days. Patients who withdraw prior to initial dose, will be replaced to ensure all 250 patients have received at least a single-dose of ciprofloxacin.

A patient will be eligible for the study once it has been determined that she meets all inclusion criteria and has none of the exclusion criteria.

5.2 Drug Supplies

5.2.1 Formulation and Packaging

The site Investigator or designee will provide the patient with a pharmacy prescription or a supply for a 3 day (250 mg BID) course of generic ciprofloxacin for the treatment of their uUTI.

5.2.2 Preparation and Dispensing

The patient will receive one 3-day treatment course of generic ciprofloxacin, with instructions to take one tablet or capsule of oral ciprofloxacin 250 mg twice daily beginning day 1 through 3 (+ 1 day).

In the event a patient's first dose is taken in the PM on Day 1, the patient will be expected to take an AM dose on Day 4 to receive the 6 doses of ciprofloxacin, and the EOT visit will occur on day 4 instead of day 3.

5.2.3 Compliance

All patients should be informed that compliance with taking all oral medication as instructed is imperative. A site designee will phone the patient or the pharmacy on Day 1 to ensure that the prescription of ciprofloxacin was picked up and the first dose was taken. This phone call should be documented in the patient's source and include the date and estimated time the patient took the initial dose.

Patients will receive a dosing diary on Day 1 and asked to record the dosing administration for the duration of the treatment period.

The total amount of oral dosing completed during the treatment period will be documented in the CRF.

5.3 Drug Storage and Drug Accountability

Drug should be stored by the patient according to the guidance provided by the site or pharmacy. For drug accountability, the site will provide the patient with a diary to collect daily ingestion of ciprofloxacin. The patient should return the diary to the clinic along with the prescription bottle/container after completion of their ciprofloxacin course of treatment. Site staff will keep diary in source and record in the CRF.

5.4 Medication(s), Adjunctive Therapy and Non-drug Therapy

5.4.1 Concomitant Medications

Any medication taken by the patient, other than ciprofloxacin, is considered a concomitant medication. Any concomitant medication which is administered from Screening through the TOC Visit must be recorded in the patient's source record.

Any concomitant medication which is an antibiotic, administered for the treatment of the primary uUTI, should also be recorded in the CRF. No other concomitant medications need to be recorded in the CRF.

At each visit, the Investigator or site designee will obtain information on any therapeutic interventions (e.g., drug and non-drug therapy, surgery, etc.) provided. The use of any investigational drug is prohibited and patients may not participate in any other studies involving other marketed products concomitantly while in this study.

The use of other (non-antibacterial) medications should be limited to those essential for the care of the patient. All medications required by the patient to manage underlying illnesses, other than the infection under study, and any drugs that may be required for emergency treatments must be recorded in the source document.

The bioavailability of ciprofloxacin is significantly reduced when co-administered with magnesium or aluminum containing antacids. As a result, co-administration of these antacids with ciprofloxacin is not permitted.

Dosing with food does not affect the overall absorption of ciprofloxacin.

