5.4.2 Concomitant Antibacterial Medications

Concomitant systemic antibacterials are prohibited during the study, up to the TOC visit, unless it has been determined that the antibacterial would not have a potential effect on outcome evaluations in patients with uUTI.

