7.2 Efficacy

7.2.1 Overall Response

Overall Response is assessed on Day 12 (+/- 1 day) TOC using the definitions listed below:

A patient will be defined as a responder if the following criteria are met (programmatically, based on the data on the CRF):

- The patient is alive
- The patient has received no rescue therapy for uUTI
 - If an antibiotic active against the urinary tract pathogen is given for other reasons, then the patient will be considered indeterminate, and analyzed as a non-responder for uUTI
- The patient has resolution of the symptoms of uUTI present at trial entry and no new uUTI symptoms
- Urine culture taken on Day 12 (+/- 1 day) demonstrates <10³ CFU/mL of the baseline uropathogen

All other patients will be considered non-responders. If data are unavailable to determine if the patient is a responder or non-responder, the patient will be considered as having an indeterminate response.

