9 DATA ANALYSIS/STATISTICAL METHODS

9.1 Sample Size Determination

The study is designed to determine the clinical and microbiologic efficacy of ciprofloxacin for adult female patients with uUTI, due to either a ciprofloxacin susceptible or non-susceptible organism. Two-hundred fifty (250) symptomatic patients will be enrolled with the expectation that there will be no screen failures. Of the 250 enrolled patients, we expect 50 will not have a positive urine culture for $\geq 10^5$ CFU/mL of a uropathogen at baseline. Of the 250 enrolled patients, we expect 40 will have a uUTI due to a ciprofloxacin non-susceptible organism.

Patients who withdraw prior to initial dose, will be replaced to ensure all 250 patients have received at least a single-dose of ciprofloxacin.

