4.5 Clinically Evaluable (CE)

Clinically evaluable is defined both at the end of treatment (EOT) and test of cure (TOC) visits.

- All patients who were included in the MITT population and meet the following criteria are clinically evaluable.
 - a) Received a minimum of four doses of ciprofloxacin.
 - b) Had no important protocol deviations that would affect the assessment of efficacy as indicated in the protocol deviation log (see section 7.9). These will be pointed out by clinical team and marked in the CE spreadsheet.
 - c) Had a Clinical response assessment of clinical cure or clinical failure (and not indeterminate) at the EOT or TOC visits (within Protocol visit window), respectively.
 Note: Since the PSAQ does not contain a date completed, the date if lab culture will be used.
 - d) Did not receive any antibiotic therapy with potential activity against any of the baseline uropathogens collected at screening between the time of the baseline culture and the EOT or TOC culture, respectively. This excludes the protocol defined study therapy and patients who were considered clinical failures and required additional antibiotic therapy. Patients with a coinfection with a gram-positive uropathogen resistant to ciprofloxacin are allowed to receive agents with narrow spectrum gram-positive coverage (i.e., such as linezolid or vancomycin).

Note: This rule will be applied through the manual review of CE spreadsheet by the sponsor.

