4.7 Determination of Inclusion in Analysis Populations

Inclusion into the ITT, MITT, m-MITT and Safety populations will be determined programmatically from the electronic case report form (e-CRF) data. Inclusion into the CE populations will be determined programmatically from the e-CRF data and through a manual review conducted by the sponsor. The sponsor will review both clinical and microbiological data for determination of criteria used to assess inclusion in the CE populations and for determination of baseline and post-baseline pathogens. The sponsor will review the data concurrent with the conduct of the study. Inclusion into the ME populations will be determined programmatically.

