5 DEFINITION OF OUTCOME MEASURES

5.1 Primary Efficacy Outcome Measure

The primary efficacy outcome is overall response assessed on Day 12 (+/- 1 day) in the m-MITT using the definitions listed below.

A patient will be programmatically defined as a responder based on the following:

- The patient is alive;
- The patient has received no rescue therapy for uUTI (if an antibiotic active against the urinary tract pathogen is given for other reasons, then the patient will be considered indeterminate, and analyzed as a non-responder);
- The patient has resolution of the symptoms of uUTI present at trial entry and no new uUTI symptoms, on Day 12 (+/- 1 day);
- Urine culture taken on Day 12 (+/- 1 day) demonstrates <10³ CFU/mL of the baseline uropathogen;

A patient will be defined as a non-responder if at least one of the following criteria is met:

- The patient has died:
- The patient has received rescue therapy for uUTI (If an antibiotic active against the urinary tract pathogen is given for other reasons, then the patient will be considered indeterminate, and analyzed as a non-responder for uUTI);
- The patient has no resolution or worsening of the symptoms of uUTI present at trial entry and/or with new uUTI symptoms;
- Urine culture taken demonstrates $\geq 10^3$ CFU/mL of the baseline uropathogen;

All other patients will be considered indeterminate, including those with missing data needed to determine if the patient is a responder or non-responder. For example, if either urine culture or uUTI symptoms are not completed, the patient will be considered an indeterminate.

For the ITT and m-MITT populations, the proportion of ITT or m-MITT patients with a responder is defined using the following formula:

Number of responders

Number of responders + Number of non-responders + Number of indeterminates

By definition, patients in the CE and ME populations must have sufficient information for determination of efficacy response. Thus, the proportion of CE and ME patients is defined using the following formula:

Number of responders + Number of non-responders

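### The primary endpoint rule needs antibiotics given for other reasons, but the CRF is only required to hold those given for the uUTI

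*Protocol*

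**What the plan says.** **The endpoint rule.** The primary outcome is overall response at Day 12 in m-MITT. Protocol 7.2.1 derives responder status "programmatically, based on the data on the CRF". SAP 5.1 is also programmatic and repeats the rule at issue: "if an antibiotic active against the urinary tract pathogen is given for other reasons, then the patient will be considered indeterminate", and is analysed as a non-responder.

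**What must be entered.** Protocol 5.4.1 requires all concomitant medication from Screening through TOC to be in the source record. For the CRF it asks for less: "Any concomitant medication which is an antibiotic, administered for the treatment of the primary uUTI, should also be recorded in the CRF". It continues: "No other concomitant medications need to be recorded in the CRF". SAP 7.4 likewise names only the source document, yet plans a summary of patients who received any antibiotic with potential activity against a baseline uropathogen.

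**Related controls.** Protocol 5.4.2 limits the exposure: "Concomitant systemic antibacterials are prohibited during the study, up to the TOC visit", except where a drug is judged unable to affect the outcome evaluation. SAP 4.5 has an antibiotic criterion for clinical evaluability, and notes: "This rule will be applied through the manual review of CE spreadsheet by the sponsor". SAP 7.9 removes deviations that affect the analyses from the CE population.

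**The concern.** The rule concerns antibiotics given for reasons other than the uUTI. The only antibiotics that sites must enter are those given for the uUTI. The required entries therefore identify rescue therapy, but not the patients this rule was written for.

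A program reading the CRF cannot tell an antibiotic that was not entered from one that was not taken. If such a patient is alive, has had no rescue therapy, has no remaining or new symptoms and has a Day 12 culture below 10³ CFU/mL of the baseline uropathogen, she is classed as a responder. The missed drug is by definition active against her pathogen, so it may itself have produced the culture result credited to ciprofloxacin.

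This matters most in the non-susceptible subgroup. Protocol 1.2.1 presents response despite in vitro resistance as the little-studied question, and an unrecorded active antibiotic would look exactly like that. With a single arm, no control group shares the error. Because entry is optional, capture may also differ between sites.

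**Working it through.** The plan gives no figure for this point, so there is none to reproduce. The check is a trace of the data flow, then arithmetic for scale.

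**1. Does any stated route carry these data into the m-MITT endpoint?**

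| Place | What it provides | Reaches overall response in m-MITT? |
|---|---|---|
| Protocol 5.4.1 | CRF entry of antibiotics for the uUTI; all others in source | No: the antibiotics concerned need not be entered |
| SAP 7.4 | Recording in the source document; summaries of antimicrobials | No: adds no CRF requirement |
| SAP 4.5 | Sponsor's manual antibiotic review | No: CE, and ME through CE |
| SAP 4.7 | Sponsor review for CE criteria and for pathogen determination | No: antibiotic use is not covered outside CE |
| SAP 6.4 | Merge of central and local culture results | No: culture data only |
| SAP 6.5 | Missing data lead to indeterminate | No: an entry never required leaves no visible gap |
| SAP 7.8 | AE listings with action taken and outcome | No: no treating drug is listed |
| SAP 7.9 | Exclusion for deviations that affect the analyses | No: CE only |
| SAP 8 | Differences from the protocol | No: the point is not mentioned |

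The rule can thus be carried out in m-MITT only where a site has entered data it was not asked for.

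**2. Direction.** Missing the antibiotic moves a patient from non-responder to responder, or changes nothing if she fails another criterion. It cannot lower the rate.

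**3. Size per missed patient who otherwise meets the criteria.** Inputs are from Protocol 9.1 and SAP 6.1: 250 enrolled, 50 without a qualifying culture, and "Of the 250 enrolled patients, we expect 40 will have a uUTI due to a ciprofloxacin non-susceptible organism".

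- Expected m-MITT = 250 − 50 = 200. Shift = 1/200 = 0.5 points; two patients, 2/200 = 1.0 point.
- Non-susceptible, assuming all 40 are in m-MITT: 1/40 = 2.5 points.
- Remaining patients: 200 − 40 = 160; 1/160 ≈ 0.6 points.

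The 200 is an upper figure. SAP 4.4 also limits the number of species and SAP Appendix 3 restricts the organisms. A smaller denominator makes the shift per patient larger.

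**4. Range under stated assumptions.** The documents give no frequency of such antibiotic use. Let r be the share of m-MITT patients given one and not captured, and p the share of those who otherwise meet the criteria. The shift in points is 100 × r × p.

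- r = 0.5%, p = 60%: 200 × 0.005 × 0.60 = 0.6 patients, 0.3 points.
- r = 5%, p = 80%: 200 × 0.05 × 0.80 = 8 patients, 4.0 points.

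Both r and p are assumptions, so this range shows scale and is not an estimate. For comparison, the 95% half-width 1.96 × √(q(1 − q)/200), at assumed response rates q of 60% to 80%, is 6.8 to 5.5 points.

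**The case against.** The best case against has four parts.

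- **The data may exist.** Protocol 5.4.1 says other medications need not be entered, which does not bar entry, and the CRF is not among the documents. SAP 7.4 plans coded summaries of concomitant antimicrobials without limit by indication, and a listing of antibacterials from the 30 days before treatment. That suggests broader collection. This is fair, and it is why the claim is only that patients may be missed. But no section requires the entry. If the CRF does collect these drugs, Protocol 5.4.1 misdescribes it; if it does not, neither the endpoint rule nor the SAP 7.4 summary can be fully carried out.
- **Such patients would surface elsewhere.** Use of an active systemic antibacterial is prohibited, hence a deviation, and SAP 7.9 lists deviations for all patients. The illness treated may also appear as an AE. True, but nothing links either source to response classification in m-MITT. SAP 4.7 does not supply the link: its statement that "Inclusion into the ITT, MITT, m-MITT and Safety populations will be determined programmatically from the electronic case report form (e-CRF) data" concerns membership of the population, not response.
- **The effect is small.** Probably so. There is no hypothesis test to overturn, and a patient counts only if she meets every other criterion. This limits the severity but leaves the primary rule without its input.
- **One SAP sentence would do.** Extending the sponsor's antibiotic review to m-MITT would be a workable fallback, provided that the review draws on the source records. It would still leave Protocol 5.4.1 at odds with 7.2.1.

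**Conclusion.** The concern holds. As written, the plan bases a primary-endpoint rule on CRF data that sites need not enter, and no stated safeguard covers overall response in m-MITT. CE and ME are partly protected. The SAP 7.4 summary of potentially active antibiotics has the same gap.

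The bias is upward only: 0.5 points per affected patient in m-MITT, and 2.5 points in the non-susceptible subgroup. These figures rest on the planned counts of 200 and 40, and on all 40 being in m-MITT. The number of affected patients is unknown and should be small. The conflict between the sections is certain; its effect on the result depends on what the CRF actually collected. It should be fixed, because the subgroup of most interest is the most sensitive and the repair is cheap.

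**What to change.** 1. Amend Protocol 5.4.1 so that every systemic antibacterial taken from Screening through TOC, whatever its indication, is entered in the CRF with drug, dates and indication.
2. For patients already enrolled, transcribe the existing source entries before database lock.
3. State in SAP 5.1 that these entries feed the overall-response rule, and in SAP 7.4 that they feed the summary of potentially active antibiotics.

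The cost is a small CRF addition and a one-time transcription of information that sites must already hold in source. The reported response rate may fall slightly. Only data capture changes; treatment and permitted medication are untouched.
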